9.5. Outcome measures

9.5.1. Primary trial objective

The primary aim of the trial is to compare the cardiac ED visits and hospital readmission rates as well as downstream testing at 90 (+/-7) days after hospitalization for MI between group 1 and group 2.

9.5.1.1. Primary outcome measures

The combined primary endpoint of the trial is the rate of ED visits, hospital readmission, and any of the downstream testing modalities (echocardiogram, stress test or coronary CT, or invasive coronary angiogram) from discharge after index hospitalization for MI to 90 days of follow-up between group 1 and group 2.

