1. STUDY SUMMARY

Title	Home Telemonitoring In Patients after Myocardial Infarction Experience, HELP ME trial.
Methodology	
Randomized, parallel-group clinical trial in acute coronary syndrome patients which have undergone coronary angiography with two study groups:
 
Group 1: Discharged home with standard medical treatment.
 
Group 2: Discharged home with standard medical treatment and 12 lead ECG telemonitoring device for 90 days.

Overall Study Duration	2 years
Subject Participation Duration	90 days
Single or Multi-Site	Single Site Mayo Clinic Rochester, MN
Objectives	
Several retrospective studies indicate that patients with ACS post PCI have less readmissions and better survival with 12 lead ECG telemonitoring at home. So far, no prospective study was done to show this benefit.
 
The objective of the current study is to evaluate the incidence of ED visits, re-hospitalizations and major adverse cardiovascular events (MACE including cardiovascular death and hospitalization for myocardial infarction, unstable angina, repeat revascularization, heart failure, stroke, arrhythmias, and cardiac arrest), and cost-effectiveness over a period of 90 (+/- 7) days after an index hospitalization for an acute myocardial infarction (MI).
 
Our central hypothesis is that 12 lead ECG home telemonitoring decreases general and cardiac ED presentation and hospital readmission rates without an increase in MACE and at a lower health care utilization cost compared to patients with standard therapy alone.
 
Three specific aims will be pursued:
 
Aim 1: To compare the rates of ED visits and re-hospitalization rates as well as related downstream cardiovascular testing (echocardiogram, stress test or coronary CT, or invasive coronary angiogram) from discharge after index hospitalization for MI to 90 days follow-up between patients undergoing standard care alone or standard care plus the home 12 lead ECG telemonitoring device
 
Aim 2: To compare the rates of MACE from discharge after index hospitalization for MI to 90 days follow-up between patients undergoing standard care alone or standard care plus the home 12 lead ECG telemonitoring device
 
Aim 3: To compare health care cost utilization from discharge after index hospitalization for MI to 90 (+/-7) days follow-up between patients undergoing standard care alone or standard care plus the home 12 lead ECG telemonitoring device

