3. STUDY OBJECTIVES

3.1 Primary Objective

The primary objective of this trial is to compare the rates of ED visits and re-hospitalization rates as well as related downstream cardiovascular testing (echocardiogram, stress test or coronary CT, or invasive coronary angiogram) from discharge after index hospitalization for MI to 90 (+/-7) days follow-up between patients undergoing standard care alone or standard care plus the 12 lead ECG Smartheart home telemonitoring device.

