9. STATISTICAL CONSIDERATIONS

9.1. General Design Issues

This study will be conducted as a parallel group randomized clinical trial. The main goal is to define if Smartheart 12 lead ECG home device will decrease the rates of ED visits and rehospitalization in patients after index hospitalization for acute MI.

Our central primary hypothesis is that the Smartheart 12 lead ECG home device will decrease the ED visits and rehospitalization rates, leading to subsequent decrease in healthcare costs. Additional potential benefit is decrease in mortality by identifying any cardiac emergency at the early stage with appropriate urgent medical assistance. The quality of life of patients with the Smartheart device at home could be improved, knowing there is an easily available tool which can provide quick and reliable diagnosis.

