9.2. Sample Size and Randomization

Patients will be randomized to either standard medical therapy or the medical therapy plus the Smartheart 12 lead ECG home device.

The primary combined endpoint parameter is the rate of ED visits/rehospitalizations as well as related downstream cardiovascular testing (echocardiogram, stress test or coronary CT, or invasive coronary angiogram) at 90 (+/-7) days after discharge and mortality rates during the 90 (+/-7) days of follow up. Based on the most recent in-house registry data, we have about 50 AMI patients undergoing PCI a month. Accordingly, we have at least 600 patients a year who are discharged with a diagnosis of AMI from Saint Mary's Hospital.

Our own registry data further indicate that 24% of revascularized AMI patients will present to the ED or will be readmitted within 90 days. This is in keeping with the published literature citing a rate of 20-30%. Half of these patients will present for cardiovascular complaints and may get further testing, including echocardiogram, stress test or coronary CT, or invasive coronary angiogram. Having a 12-lead ECG available and the phone triage available to direct care may impact not only emergency presentation but also downstream testing. This will be considered in this trial, and each of these will be considered as a component to the combined primary endpoint event. Assuming that patients presenting with cardiovascular concern may receive two of the outlined downstream test as they present to the ED and hospital, the estimated event rate will be 48%. With 120 patients in each arm the study we would be adequately powered (beta error <0.2) to show a statistically significant (at alpha error levels of <0.05) for a 37.5% event reduction.

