9.4. Interim Analyses and Stopping Rules

Due to the uncertainty in proposed rehospitalization rate of the treatment arm, a sample size reestimation (SSR) will be performed after 60 patients have finished the study in the treatment group. The rate will be estimated only for the treatment group, and the sample size will be recalculated using the new calculated rate. The results of this calculation will be the new larger sample size for the study. If the calculation proposes a sample size that is smaller, the original 120 patients per group will be used. No stopping rules are implemented for this pilot study.

As an example, there may be more rehospitalizations and ER visits than expected in the treatment group. If the rehospitalizations and ER visits were 17.5% at 90 days, this would result in the sample size being increased to 181/group. Alternatively, if the rehospitalizations and ER visits in the treatment group were 10%, the sample size required would only be 62/group. If this were to happen, the sample size for the study would be maintained at 120 per group.

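### The primary endpoint is defined inconsistently in sections 1, 3.1, 9.2, 9.5.1 and 9.5.1.1 (death, cardiac-only ED visits, related or any testing), and 9.6 does not say which version is tested

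*Combined protocol and SAP*

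**What the plan says.** The wording differs by section of the combined protocol and SAP:

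- **9.5.1.1 Primary outcome measures** gives this wording: "The combined primary endpoint of the trial is the rate of ED visits, hospital readmission, and any of the downstream testing modalities". There is no death, no cause limit and no word tying the test to a presentation.
- **9.2 Sample Size and Randomization:** ED visits or rehospitalizations and *related* testing, "at 90 (+/-7) days after discharge and mortality rates during the 90 (+/-7) days of follow up".
- **9.5.1 Primary trial objective:** "compare the cardiac ED visits and hospital readmission rates as well as downstream testing". Death is absent.
- **3.1 Primary Objective:** "ED visits and re-hospitalization rates as well as related downstream cardiovascular testing". Death is absent. Aim 1 in section 1 matches it: "To compare the rates of ED visits and re-hospitalization rates as well as related downstream cardiovascular testing".
- **9.6 Data Analyses:** a chi-square test on the primary combined endpoint, with no list of components and no cross-reference.

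Two other sections leave testing out. The main goal in 9.1 is to find whether the device "will decrease the rates of ED visits and rehospitalization in patients after index hospitalization for acute MI". The sample size re-estimation in 9.4 uses rehospitalizations and ER visits: "If the rehospitalizations and ER visits were 17.5% at 90 days, this would result in the sample size being increased to 181/group".

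Under 8.1.2 the patient and the treating cardiologist are told the assigned group. Section 13 rules out an adjudication committee.

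**The concern.** Sections 9.2 and 9.5.1.1 both define something that the label in 9.6 fits, and they differ on death and on testing. A patient who dies at home with no ED visit, readmission or test is an event under 9.2 and event-free under 9.5.1.1. A routine outpatient echocardiogram counts under a literal reading of 9.5.1.1 but not under *related*. An ED visit for a non-cardiac complaint counts everywhere except in 9.5.1.

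One dataset can therefore give more than one primary result. The plan has no rule for calling a visit cardiac or a test related, no adjudication, and no blinding of patient or treating cardiologist. Nothing in it stops the version from being settled after the arms and results are known.

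**Working it through.** **Inputs.** From 9.2: 24% of patients present to the ED or are readmitted by 90 days; half of these (12%) present for cardiovascular complaints; each of those may have two tests; reduction 37.5%; 120 per arm; alpha 0.05, taken as two-sided; no dropout. From 9.4: 181 and 62 per group.

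**Formulas.** With p̄ = (p1 + p2)/2:
- Power = Φ{[|p1 − p2|√n − 1.96√(2p̄(1 − p̄))] / √[p1(1 − p1) + p2(1 − p2)]}
- n per arm for 80% power = [1.96√(2p̄(1 − p̄)) + 0.8416√(p1(1 − p1) + p2(1 − p2))]² / (p1 − p2)²

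**1. The plan's own figure.** 24% + 2 × 12% = 48%, and 48% × 0.625 = 30%. Power = Φ[(1.972 − 1.352)/0.678] = Φ(0.914) = 82%. The claim in 9.2 of beta below 0.2 reproduces.

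**2. Any-cause against cardiac.** Section 9.5.1 limits ED visits. Non-cardiac presentations make up 24% − 12% = 12 points, and the documents do not say how many are ED-only. Disagreement is the share of 1,000,000 simulated trials in which the two versions, scored on the same patients (cardiac events a subset of all events), differ on significance favouring the device. The plan's 48% and 30% are treated as patient proportions.

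| Share of the 12 points removed | Rates | Power | Disagreement |
|---|---|---|---|
| 25% (assumed) | 45% vs 28.1% | 78% | 8% |
| 75% (assumed) | 39% vs 24.4% | 68% | 18% |
| 100% (readmissions limited too) | 36% vs 22.5% | 63% | 23% |

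**3. Related against any testing.** This is done per patient. If tests arise only in patients who present, the related version stays at 24% vs 15%. If a share t of otherwise event-free patients in both arms has a routine test (assumed), the any version is 24% + 76% × t against 15% + 85% × t.

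| t | Rates, any version | Power, any version | Disagreement with related |
|---|---|---|---|
| 1% | 24.8% vs 15.9% | 40% | 7% |
| 5% | 27.8% vs 19.3% | 34% | 16% |
| 10% | 31.6% vs 23.5% | 29% | 22% |
| 40% | 54.4% vs 49.0% | 13% | 37% |

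The baseline for this table is the 42% power of step 6, not 82%.

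**4. No true effect.** Taking the better of the any-cause and cardiac versions raises the chance of a false result favouring the device from about 2.5% to about 3.8% (36% nested in 48%) or 4.3% (12% nested in 24%). Both figures use the version that limits readmissions too; limiting ED visits alone inflates it less.

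**5. Deaths (exact binomial).** Adding 1, 2 or 3 otherwise event-free deaths to each arm loses significance in 0.2%, 0.5% or 0.8% of trials at 48% vs 30%, and in 1.3%, 2.6% or 3.7% at 24% vs 15%. At 48% vs 30%, if all fall in the device arm 4-13% lose it; if all fall in control 3-8% gain it.

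**6. A separate fault in 9.2.** The text reads "may receive two of the outlined downstream test as they present to the ED and hospital, the estimated event rate will be 48" percent. That adds tests to presentations in the same patients, so 48% is a sum of events, while a chi-square test needs patients. If tests occur only in patients who present, the rates are 24% vs 15%: power = Φ[(0.986 − 1.098)/0.557] = Φ(−0.202) = 42%, with 304 per arm for 80%.

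**7. The basis of 9.4.** A 30% control rate gives 180.8 and 61.6 per arm at treated rates of 17.5% and 10%, which round up to the stated 181 and 62. A 24% control rate gives 610 and 112; 48% gives 36 and 22. So 9.4 uses neither rate on which 9.2 builds its calculation, although 30% is the top of the 20-30% literature range cited there.

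**The case against.** The best defence is that 9.5.1.1, under the heading for primary outcome measures, is the formal definition and the rest is loose summary. The central hypothesis in section 1 covers both general and cardiac presentations, and 3.2(a) and 9.5.2.1 make the cause split secondary, so *cardiac* in 9.5.1 looks like a slip. *Any* may mean only any one on the list, and *downstream* already suggests a test that follows a presentation. Much of this stands, and it makes 9.5.1.1 the natural base for one definition. But no text says that it governs. Section 9.2 states its own definition under an equivalent label and carries the power calculation, and 9.5.1.1 still omits both *related* and death.

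A reader might count 9.1 and 9.4 as further rival endpoints. The documents do not support that: 9.1 states a goal and hypothesis, 9.4 an input to sample size re-estimation, and the word combined in 9.6 excludes both. Section 9.4 is a sizing inconsistency.

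A reader might also infer that the cardiac wording must lose power. If the whole 18-point reduction is in cardiac events (36% vs 18%), that version, with readmissions limited too, has 89% power. The two still disagree in 13% of trials.

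**Conclusion.** The inconsistency is on the page and should be resolved before any outcome comparison. It concerns death, the cardiac limit on ED visits, and related or any testing, across sections 1, 3.1, 9.2, 9.5.1 and 9.5.1.1, with 9.6 silent on the choice. The test wording and the cause wording matter most. Their size depends on the ED-only share and the routine-test rate, neither of which the documents give.

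Three larger conclusions might be inferred and are not supported:

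- **That the choice of wording takes power from 82% to 42%.** That fall comes from counting events as patients in 9.2 and would remain under consistent wording.
- **That the disagreement rates are false-positive rates.** They assume a true effect. The one-sided inflation for the cause wording is from about 2.5% to at most about 4.3%.
- **That omitting death favours the device.** Nothing shows which arm event-free deaths would fall in, and balanced deaths change little.

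**What to change.** Before any outcome comparison:

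1. Adopt one patient-level definition with 9.5.1.1 as its base: the proportion of patients with at least one component event from discharge to the day-90 follow-up. State one window; 9.5.1.1 gives 90 days, 3.1 and 9.2 give 90 (+/-7), and 10.3.4 times the final contact from randomization. Use the definition word for word in sections 1, 3.1, 9.2, 9.5.1 and 9.5.1.1, and cite it in 9.6.
2. Delete *cardiac* from 9.5.1.
3. On testing, choose one rule. Either any listed test counts, with its expected routine rate stated, or only tests arising from an ED visit or stay count. The second rule adds no patients to the primary endpoint, and the text should say so, because 9.2 treats each test as a component.
4. On death, choose one rule. Either count all-cause death as an event, or remove mortality from 9.2, say how deaths are handled, and list all-cause death as a secondary outcome. In both cases add all-cause death to the day-90 follow-up: the call in 8.1 lists MACE, which section 1 limits to cardiovascular death. The death table in Appendix A sits in a generic template and does not settle capture.
5. Restate the event rate and power in 9.2, and the rate and examples in 9.4, for the definition chosen.

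The cost is wording, one vital-status item, and a less favourable stated power: about 42% at 120 per arm if tests occur only in patients who present.

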6.2 Exclusion criteria

- <18 years of age
- No ability to use the device at home / Unable to comply with the device instructions
- No smartphone device or home wi-fi/mobile internet which prevent 24/7 ability to transmit ECG
- Unable to download the smartheart application
- No support in home environment
- Out of hospital cardiac arrest
- Resident of nursing home or acute care facility
- Uninterpretable ECG at discharge – left bundle branch block, pacemaker dependence, implantable cardioverter defibrillator.
- Out of hospital cardiac arrest: secondary to a non-shockable rhythm, unrelated to an acute coronary syndrome, or with any level of neurologic damage.
- Patients who are planned for staged PCI after the index hospitalization

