8.1.2 Enrollment, Baseline, and/or Randomization

All patients who consent to the study are considered to be enrolled as of the date of the consent.

Baseline Assessments- comprises a review for any cardiovascular diseases or risk factors, home medications. Additional data will be collected: type of AMI (location: anterior, inferior, posterior, lateral), troponin levels, baseline ECG, left ventricular function by echocardiography, Canadian Classification scale (CCS) of Angina(class I, II, III IV) .

Randomization- will be done once all inclusion and exclusion criteria are reviewed and the patient meets eligibility criteria. Patient and treating cardiologist will be informed which study group the patient was assigned. Patients assigned to group 1 will be discharged with standard medical therapy as indicated by AHA/ACC guidelines in post AMI patients treated with or without PCI. Patients in group 2 will be discharged with the standard medical treatment as indicated by AHA/ACC guidelines in post AMI patients treated with or without PCI plus they will receive the Smartheart 12 lead ECG home telemonitoring device for the period of 90 days (+/-7). Those patients will have short explanation on how the device works, how to adjust it on the chest and how to transmit the ECG.

A post-study questionnaire will be administered to patients randomized to the device group to collect feedback on their experiences with the device. Participation is voluntary, and responses will be anonymized to ensure confidentiality. The inclusion of this questionnaire will not impact the primary study objectives or patient safety.

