8.1 Schedule of Evaluations

Assessment	Screening, Enrollment, Randomization: pre-discharge (Day 0)	Week 1 (-3,+6 days)	Week 2 (-3,+6 days)	Week 4 (-3, +6 days)	Day 90 (Final) (+/- 7 days)
Informed Consent Form	X (R)				
Demographics	X				
Medical History	X				
Vital signs	X				
Physical Examination	X				
Current Medications	X				
Blood Chemistries	X				
Electrocardiogram	X				
Echocardiogram	X*				
Inclusion/Exclusion Criteria	X (R)				
Enrollment/ Randomization	X (R)				
Providing Device + Instructions	X (R)				
Quality of Life questionnaire (day 0)	X (R)				
Follow-up ECG and training call		X (R.S.)	X (R.S.)	X (R.S.Q)	
End of participation phone call, will include:					X (R)
• ED visits/Hospitalizations/MACE data /ccs					X (R)
• Current medications and if changed lately					X (R)
• Quality of Life questionnaire (day 90)					X (R)
Device collection (patient sending by mail)					X (R)

X Performed as standard of care (not specific for research)

X* If performed after the AMI event and pre-discharge

X (R) Research related only

X (R.S.) Research – Study group related only

X (R.S.Q) Research – Study group related only, depends on the need of further training beyond the first two tests.

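### The primary endpoint definition in 9.5.1.1 counts planned readmissions and any listed test, which is broader than the related, presentation-driven events behind the 48% in 9.2

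*Combined protocol and SAP*

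**What the plan says.** Section 9.5.1.1 is the operative definition: "The combined primary endpoint of the trial is the rate of ED visits, hospital readmission, and any of the downstream testing modalities". The modalities are echocardiography, stress testing, coronary CT and invasive angiography, counted from discharge to 90 days. The section does not ask that a test follow from an ED visit, an admission or a symptom, and it does not separate planned from unplanned readmissions.

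Other sections word the endpoint differently:

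- Aim 1 in section 1, section 3.1 and section 9.2 confine testing to *related* tests. None of them defines the word. Section 9.2 also adds mortality.
- Section 9.5.1 refers to cardiac ED visits and leaves *related* out.
- Section 9.2 derives the event rate by assuming that patients with a cardiovascular concern "may receive two of the outlined downstream test as they present to the ED and hospital".

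No version limits readmissions to unplanned ones. The one provision on planned care is an exclusion criterion (sections 1 and 6.2): "Patients who are planned for staged PCI after the index hospitalization".

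On who can influence events, section 8.1.2 says: "Patient and treating cardiologist will be informed which study group the patient was assigned". Section 13 states that no adjudication committee will be convened. Section 9.6 compares the combined endpoint between arms by chi-square test.

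**The concern.** The intervention works through symptoms. Under sections 4.2 and 5 a patient with symptoms transmits an ECG, and a reassuring tracing with low suspicion leads to advice against an unnecessary ED visit. That process cannot avert an admission or a test already booked when the patient left hospital. Under the literal wording of 9.5.1.1, such a patient is a primary event in either arm whatever the device does.

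Two things follow. First, these events add equally to both arms and pull the two proportions together, although the sample size makes no allowance for them. Second, the treating cardiologist, who can order tests, knows the allocation. Discretionary testing could then differ by arm for reasons unrelated to triage, and nobody is named to decide which tests are *related*.

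**Working it through.** **Inputs, all from 9.2 unless noted**

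- Sample size: "With 120 patients in each arm"; 1:1 allocation (9.3).
- Type I error: "at alpha error levels of <0.05". Sidedness is not stated; two-sided is assumed.
- Target power: at least 80% (beta below 0.2).
- Control rate 48%, relative reduction 37.5%, so the device-arm rate is 0.48 × (1 − 0.375) = 0.30.
- Build-up of the 48%: 24% present to the ED or are readmitted, half of them (12%) for cardiovascular complaints, with two tests each: 24% + 2 × 12% = 48%. Nothing in this sum stands for a test outside a presentation.

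**Step 1: reproduce the plan's power**

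Power = Φ{[|p1 − p2|√n − 1.96√(2p̄(1 − p̄))] / √(p1(1 − p1) + p2(1 − p2))}, where p̄ is the mean of the two rates.

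With p1 = 0.48, p2 = 0.30, p̄ = 0.39, n = 120:

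- |p1 − p2|√n = 0.18 × 10.954 = 1.972
- 1.96 × √(2 × 0.39 × 0.61) = 1.352
- √(0.2496 + 0.2100) = 0.678
- (1.972 − 1.352) / 0.678 = 0.914, so power is 82.0%

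The stated power reproduces. The minimum for 80% is 115 per arm, so there is little slack.

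**Step 2: add events that triage cannot prevent**

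Assumption: a share r of patients in each arm has a qualifying planned admission or routine test by day 90, independent of other events. Each rate becomes r + (1 − r)p. For r = 5%: 0.05 + 0.95 × 0.48 = 0.506 and 0.05 + 0.95 × 0.30 = 0.335. The documents give no r, so a range is shown.

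| r | Control | Device | Relative reduction | Power at 120 per arm | n per arm for 80% |
|---|---|---|---|---|---|
| 0 | 48.0% | 30.0% | 37.5% | 82.0% | 115 |
| 5% | 50.6% | 33.5% | 33.8% | 76.9% | 130 |
| 10% | 53.2% | 37.0% | 30.5% | 71.5% | 147 |
| 20% | 58.4% | 44.0% | 24.7% | 60.8% | 188 |

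**Step 3: does the direction depend on the starting point?**

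- *Planned readmissions may already be in the registry 24%.* Adding r would then count them twice. The alternative is to hold control at 48% and let a share s of those events be unpreventable. With s = 10%, the device rate is 0.48 × (0.10 + 0.90 × 0.625) = 31.8% and power is 72.9%. With s = 25%, it is 34.5% and 56.6%.
- *The 48% is an event count, not a patient proportion.* Tests are added to patients already counted as presenters. If tests occur only in presenters, the patient-level comparison is 24% versus 24% × 0.625 = 15%, and power is 42.0% before any dilution. With r = 5%, 10% and 20% on top, it is 34.4%, 28.8% and 21.3%. That is a separate weakness; it changes the level of power here, not the direction.

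**The case against.** The strongest reply is that the plan does restrict testing. Aim 1, 3.1 and 9.2 all say *related*, and on that wording a pre-arranged test is not plainly an event. This stands: for tests, the fault is a conflict between sections and an undefined term. It does not reach readmissions, which no section limits to unplanned ones. The cardiac qualifier in 9.5.1 concerns cause, so a planned cardiac admission still counts.

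A reader might infer that routine care fills both arms with events and hides the device effect. The documents do not support that. They give no rate of planned admissions or routine tests, the schedule in 8.1 requires no imaging after discharge, and planned staged PCI is excluded.

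A reader might also infer from the echocardiogram footnote in 8.1, "X* If performed after the AMI event and pre-discharge", that patients discharged without an echocardiogram become events at their first outpatient one. The footnote only marks a pre-discharge standard-of-care item, and 8.1.2 lists left ventricular function by echocardiography among the baseline data. Nothing says how many patients leave without one.

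Counting all use is partly deliberate: the central hypothesis covers general as well as cardiac presentations, and cost. Components are also reported separately. But 9.5.2.1 splits by cardiovascular cause, not by planned status, so it does not repair the primary test.

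The sample size re-estimation in 9.4 could raise n, and the fixed 120 per arm above ignores it. Its worked examples, however, concern rehospitalizations and ER visits, not tests, and it updates only the treatment-group rate, whereas dilution raises both.

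Finally, a careless remedy could add bias. Only the device arm has the study NP/PA call channel (section 5), so counting tests prompted by a symptom call would favour detection in that arm. This objection is accepted in the fix.

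**Conclusion.** The point holds in a limited form. Section 9.5.1.1 is broader than the objective and than the sizing assumption; *related* is undefined; and planned readmissions count under every version. Following 9.5.1.1 literally would dilute the treatment difference and leave the endpoint open to unblinded test ordering without adjudication.

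The size cannot be established from the documents. On the plan's own 48% versus 30%, a 5% share of unpreventable events in each arm is enough to take power below the 80% target, and 20% takes it to about 61%. These figures assume a two-sided 5% test, equal r in both arms, independence from other events, no increase from re-estimation, and the 48% read as a patient-level rate. They are illustrative. The calculation covers dilution only; it does not quantify any difference in ordering between arms.

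**What to change.** Use one definition in 3.1, 9.2, 9.5.1 and 9.5.1.1, and bring Aim 1 in section 1 into line. A patient has a primary event if, by day 90, there is any of:

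- an ED visit;
- an unplanned hospital readmission;
- a listed test performed during an ED visit or unplanned admission, or ordered at one.

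Apply the same rule in both arms, and do not count a test on the basis of a study NP/PA symptom call alone. The same edit should settle the cardiac qualifier in 9.5.1 and the mortality component in 9.2, which the other sections do not share.

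Add a baseline CRF line, completed before allocation is revealed, listing every test and admission already planned at discharge. Items on that list are not primary events. Keep all tests and all readmissions, planned or not, as the existing secondary outcomes (3.2 a and b, 9.5.2.1).

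The cost is protocol wording and one CRF line. The remaining burden is that tests arranged after discharge must be classified from the order. This should be done from records, with the arm masked where possible.
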